13.5 Reporting and Exclusions

- 13.5.1 Evaluation of toxicity: All patients will be evaluable for toxicity from the time of their first treatment with entinostat/ Pembrolizumab (MK-3475).
- 13.5.2 Evaluation of response: All patients included in the study will be assessed for response to treatment, even if there are major protocol treatment deviations or if they are ineligible. Each patient will be assigned one of the following categories: 1) complete response, 2) partial response, 3) stable disease, 4) progressive disease, 5) early death from malignant disease, 6) early death from toxicity, 7) early death because of other cause, or 9) unknown (not assessable, insufficient data). [Note: By arbitrary convention, category 9 usually designates the “unknown” status of any type of data in a clinical database.]

All of the patients who met the eligibility criteria (with the possible exception of those who received no study medication) should be included in the main analysis of the response rate. Patients in response categories 4-9 should be considered to have a treatment failure (disease progression). Thus, an incorrect treatment schedule or drug administration does not result in exclusion from the analysis of the response rate. Precise definitions for categories 4-9 will be protocol specific.

All conclusions should be based on all eligible patients. Sub-analyses may then be performed on the basis of a subset of patients, excluding those for whom major protocol deviations have been identified (e.g., early death due to other reasons, early discontinuation of treatment, major protocol violations, etc.). However, these sub-analyses may not serve as the basis for drawing conclusions concerning treatment

efficacy, and the reasons for excluding patients from the analysis should be clearly reported. The 95% confidence intervals should also be provided.

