Definition of DLT: DLT will be defined as the occurrence of any of the following during the first 2 cycles of combined therapy unless the event can clearly be determined to be unrelated to the study drugs.

- Any grade 3 or 4 non-hematologic toxicity with the following exceptions: A) Transient laboratory abnormalities that can be treated or resolve to grade 2 or less within 72 hours.
- Grade 4 hematologic toxicity, including treatment-associated aplasia lasting >42 days from the last dose of study drug. Given that severe anemia, neutropenia and thrombocytopenia are features of advanced MDS and commonly encountered in this patient population, they will not be used to define DLT except if associated with prolonged treatment-associated aplasia as described above.
- Patients with grade 3 immune related adverse events will be removed from the treatment and this will be considered to be a DLT as well as any other immune-related adverse event that results in pembrolizumab interruption, dose modification, or discontinuation of therapy.
-
- Definition of secondary outcomes/endpoints: Overall response rate (ORR: The sum of rates of complete response [CR], partial response [PR], and hematologic improvement [HI]) as defined by the modified IWG-2006 criteria (**Appendix A**) with a goal of at least 20% to be considered clinically meaningful for further evaluation in larger studies.
- Analytic plan for primary objective: Toxicities will be tabulated and graded according to the Common Terminology Criteria for Adverse Events Version 5 (CTCAE-5). DLT will be assessed after the first 2 cycles of combined therapy.

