One of the HDACs studied in MDS is entinostat: an orally bioavailable, isotype-selective class 1-specific HDACi with long half-life (100 hours). A phase I clinical trial published in abstract form at Johns Hopkins University combined entinostat with a lower dose, prolonged administration schedules of azacitidine²². In this trial, patients were treated with SQ azacitidine for 10 days at different dose levels (30, 40, or 50mg/m²/day) and given oral entinostat (2, 4, 6, 8 mg/m²/dose) on days 3 and 10. Out of 31 enrolled patients, 13 had MDS, 4 had chronic myelomonocytic leukemia (CMML), and 14 had acute myeloid leukemia (AML). Patients were evaluable for response if they received 4 or more cycles of treatment. Of the 27 evaluable patients, 12 had responses (2 CR, 4 had partial responses [PR], and 6 bilineage hematologic improvement [HI]) according to the International Working Group [IWG] 2000 criteria. The 50mg/m²/day dose of azacitidine D1-10 and the entinostat 4 mg/m²/dose on D3 and D10 were subsequently studied in the randomized phase 2 ECOG1905 study versus azacitidine monotherapy at the same 50mg/m²/day dose D1-D10²³. Both arms achieved rates of trilineage hematologic normalization (32% for azacitidine monotherapy and 27% for combination) that were exceeded that of the historical control in which the standard regimen of azacitidine at 75mg/m²/day D1-7 was used (16% in CALBG9221 trial). While there was no survival advantage with the combination compared to azacitidine, this could be potentially related to pharmacologic antagonism caused by early administration of entinostat, a potent cell-cycle inhibitor with a long half-life of 4.5 days, in each cycle (day 3) which could have inhibited incorporation of azacitidine into DNA and subsequent cell cycling²³. These findings suggest that while entinostat has a modest activity in MDS, HMAs might not be the best choice

for combination-based regimen with entinostat. Exploration of alternative agents to combine with entinostat in the post-DNMTi failure setting might be a more rational approach.

Rationale for use of immune-check point inhibitors in MDS after DNMTi failure

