11.2 Response criteria

Myelodysplastic syndrome (MDS)

Responses for MDS patients will be defined as in the modified IWG-2006 criteria ([Appendix A1](#) and [Appendix A1](#)). These response criteria do not apply to AML as these patients are required to be in full remission by eligibility criteria. Only relapse and survival as measured by PFS and overall survival will be measured to assess response for AML patients. The OS and PFS will be measured for both AML and MDS as described in [Appendix A1](#) and [Appendix A2](#).

Duration of response: The duration of overall response is measured from the time measurement criteria are met for CR or PR (whichever is first recorded) until the first date that recurrent or progressive disease is objectively documented (taking as reference for progressive disease the smallest measurements recorded since the treatment started).

Duration of stable disease: Stable disease is measured from the start of the treatment until the criteria for progression are met.

Chronic Myelomonocytic Leukemia (CMML)

The definitions below are consistent with those detailed by Cheson, et al for MDS⁶¹ except that, as discussed earlier, for disease progression based on BM blast percentage, the patient must exceed 10% absolute BM blast percentage in addition to increasing above 50% of BM blast percentage at baseline to count as disease progression.

Complete response is defined by bone marrow showing <5% myeloblasts with normal trilineage maturation without dysplasia. When erythroid precursors constitute <50% of marrow cells, the blast percentage is based on total nucleated cells; otherwise, the blast percentage is based on non-erythroid compartment. Peripheral blood criteria consist of Hemoglobin \geq 11 gm/dl, ANC \geq 1 x 10⁹/L, Platelets \geq 100 x 10⁹/L, absence of peripheral blood blasts, all in the absence of transfusions and growth factors.

Partial response is defined by all of the above criteria with the exception of bone marrow blasts decreasing by >50% from pretreatment levels and/or achievement of a less advanced MDS FAB classification.

Stable Disease is defined by failure to achieve PR but without progression for at least 2 months.

Progression is defined according to initial blast percentages:

For patients with <5% blasts: \geq 50% increase in blasts to >10%

For patients with 5-10% blasts: \geq 50% increase in blasts to >10%

For patients with >10-20% blasts: \geq 50% increase in blasts to >20%

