Assessment of response will occur after 4 combination cycles and similar to part 1, those who achieve an objective response or SD will continue to receive the therapy till progression. Patients who progress or respond and subsequently lose response will be withdrawn from study. BM biopsy/aspirate and PB samples will be done at baseline, after first cycle of ENT monotherapy, every 2 cycles of combined therapy, and at time of progression or study discontinuation. Formal safety assessment will be performed after the first 6 patients are enrolled and each have received at least 5 cycles (i.e. 1 ENT monotherapy cycle and 4 cycles of combined therapy (DL1, DL2) for each patient) to assess for any unexpected autoimmune or other toxicity.

Primary Endpoint(s): MTD will be defined by the occurrence of DLT among 2 dose schedules (see section 5.2)

Definitions of DLT: see section 5.2

The following early stopping rule for excess toxicity in the expansion cohort will be used: We will cease enrollment in the expansion phase at the dose determined from dose escalation part of the study if we observe two or more DLTs among the first six evaluable patients enrolled in the expansion cohort. An evaluable patient is any patient who received a study drug. If the true toxicity rate is 50% or greater at the MTD then this rule will stop the trial with probability at least .89. Similarly, if the true toxicity rate is 33% at the MTD then this stopping rule will end the trial with probability .65. In that event, a new expansion cohort will

start at the dose level immediately below the dose level that was expanded. If the dose level being expanded is dose level -1, then the study will be terminated.

Secondary Endpoint(s): Overall response rate (CR, PR, and HI) as defined by the modified International working group 2006 (IWG-2006) criteria for CR, PR, HI ([Appendix A1](#) and [Appendix A2](#)) with at least 15% to be continued

Exploratory Endpoint(s):

- Median response duration for responders, median time of progression to AML, median overall survival (OS) and 1- and 2-year OS rate
- Assessment of the dynamic quantitative change in proportion of MDSCs in BM with combined therapy (target of reducing to <10%) and correlation with any observed clinical responses

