RESPONSE CRITERIA FOR ALTERING NATURAL HISTORY OF MDS**

Category	Response criteria (responses must last at least 4 weeks)
Complete remission	Bone marrow: $\leq 5\%$ myeloblasts with normal maturation of all cell lines* Persistent dysplasia will be noted*† Peripheral blood‡ Hgb ≥ 11 g/dL Platelets $\geq 100 \times 10^9/L$ Neutrophils $\geq 1.0 \times 10^9/L^†$ Blasts 0%
Partial remission	All CR criteria if abnormal before treatment except: Bone marrow blasts decreased by $\geq 50\%$ over pretreatment but still $> 5\%$ Cellularity and morphology not relevant
Marrow CR [†]	Bone marrow: $\leq 5\%$ myeloblasts and decrease by $\geq 50\%$ over pretreatment [†] Peripheral blood: if HI responses, they will be noted in addition to marrow CR [†]
Stable disease	Failure to achieve at least PR, but no evidence of progression for > 8 wks
Failure	Death during treatment or disease progression characterized by worsening of cytopenias, increase in percentage of bone marrow blasts, or progression to a more advanced MDS FAB subtype than pretreatment
Relapse after CR or PR	At least 1 of the following: Return to pretreatment bone marrow blast percentage Decrement of $\geq 50\%$ from maximum remission/response levels in I granulocytes or platelets Reduction in Hgb concentration by ≥ 1.5 g/dL or transfusion dependence
Cytogenetic response	Complete Disappearance of the chromosomal abnormality without appearance of new ones Partial At least 50% reduction of the chromosomal abnormality For patients with:
Disease progression	

Less than 5% blasts: $\geq 50\%$ increase in blasts to $> 5\%$ blasts
5%-10% blasts: $\geq 50\%$ increase to $> 10\%$ blasts
10%-20% blasts: $\geq 50\%$ increase to $> 20\%$ blasts
20%-30% blasts: $\geq 50\%$ increase to $> 30\%$ blasts

Any of the following:

At least 50% decrement from maximum remission/response in granulocytes or platelets
Reduction in Hgb by ≥ 2 g/dL
Transfusion dependency

Survival	Endpoints: Overall: death from any cause Event free: failure or death from any cause PFS: disease progression or death from MDS DFS: time to relapse Cause-specific death: death related to MDS
----------	--

To convert hemoglobin from grams per deciliter to grams per liter, multiply grams per deciliter by 10.

MDS indicates myelodysplastic syndromes; Hgb, hemoglobin; CR, complete remission; HI, hematologic improvement; PR, partial remission; FAB, French-American-British; AML, acute myeloid leukemia; PFS, progression-free survival; DFS, disease-free survival.

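### Hematologic improvement counts as a response in the ORR, but the response categories in 13.5.2 and the response-duration definition in 11.2 leave it out

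*Combined protocol and SAP*

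**What the plan says.** **Response rate.** Section 13.1 gives the secondary endpoint as "Overall response rate (CR, PR, and HI) as defined by the modified International working group 2006 (IWG-2006) criteria". The statistical methods in the synopsis and Section 13.4 also include HI. Section 13.4 adds that CR, PR and HI rates will each be reported by cohort with an exact 95% confidence interval.

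**Patient-level categories.** Section 13.5.2 states: "Each patient will be assigned one of the following categories: 1) complete response, 2) partial response, 3) stable disease, 4) progressive disease". The remaining codes are three kinds of early death and unknown. HI is not on the list. The section goes on: "Patients in response categories 4-9 should be considered to have a treatment failure (disease progression". It does not say which categories are responses.

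**Stable disease.** Appendix A1 defines it as "Failure to achieve at least PR, but no evidence of progression" for more than 8 weeks. Appendix A2, a separate table, defines HI, requires it to last at least 8 weeks, and gives criteria for losing it.

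**Duration.** Section 11.2 states: "The duration of overall response is measured from the time measurement criteria are met for CR or PR (whichever is first recorded"). Median response duration among responders is an exploratory endpoint in the synopsis and in Section 13.1.

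**The concern.** A patient whose only benefit is HI is a responder under 13.1 and 13.4. Under 13.5.2 the same patient has no code except stable disease, and under 11.2 no date on which the response begins. Two things follow.

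- The median response duration would describe CR and PR patients only, while the ORR beside it describes a wider group. Both would be labelled as results for responders.
- Responder status is ambiguous wherever it is used patient by patient: in the main response analysis of 13.5.2, in the comparison of MDSC levels between responding and non-responding patients (13.4 and Appendix J, Aim 1), and in the response by PD-L1 table (Appendix J, Aim 2).

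The decision rule makes coding matter. Two responses reject the 1% null rate. With one CR and one HI-only patient in the trial, the rule is met if HI counts and not met if only CR and PR count.

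**Working it through.** **Step 1. Follow one HI-only patient through the text.** Suppose the patient meets Appendix A2 for at least 8 weeks, never reaches CR or PR, and does not progress.

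| Place | Treatment of this patient |
|---|---|
| Synopsis, 13.1, 13.4 | Responder, counted in the ORR |
| 13.5.2 with Appendix A1 | Stable disease (category 3): not among the failures (4-9), and not called a response |
| 11.2 | No start date for response duration |
| Appendix A2 | Loss-of-HI criteria exist, but 11.2 does not use them |

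**Step 2. Reproduce the plan's operating characteristics.** Inputs from Section 13.2: n from 21 to 27, reject if 2 or more responses, null rate 1%, alternative 15%, one-sided exact binomial.

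P(X ≥ 2) = 1 − (1−p)^n − n·p·(1−p)^(n−1)

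- n=21, p=.15: 1 − .0329 − .1221 = .845
- n=27, p=.15: 1 − .0124 − .0592 = .928
- p=.01: .0185 at n=21 and .0297 at n=27

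These agree with the stated power of .84 to .93 and significance level of .02 to .03. The rule works as stated when HI is counted.

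**Step 3. Size of the gap in the duration endpoint.** At a true ORR of 15%, expected responders number 21 × .15 = 3.15 or 27 × .15 = 4.05. If a share s is HI-only, those with a start date under 11.2 number 3.15 × (1−s) or 4.05 × (1−s).

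**Step 4. What a CR+PR count would do to the rule.** No section prescribes this count; it bounds the effect of a misreading. The rate becomes .15 × (1−s). For s = 50% and n=21, p = .075 and P(X ≥ 2) = 1 − .1945 − .3312 = .474.

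| Assumed HI share s | CR+PR rate | Expected responders with a duration, n=21 / n=27 | P(X ≥ 2), n=21 / n=27 |
|---|---|---|---|
| 0 | .150 | 3.15 / 4.05 | .84 / .93 |
| 25% | .1125 | 2.36 / 3.04 | .70 / .82 |
| 1/3 | .100 | 2.10 / 2.70 | .64 / .77 |
| 50% | .075 | 1.58 / 2.03 | .47 / .61 |
| 2/3 | .050 | 1.05 / 1.35 | .28 / .39 |

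The documents give no expected HI share for this regimen. In the entinostat plus azacitidine study described in Section 2.1, 6 of 12 responses were HI, which is the 50% row. That study had a different partner drug, a mix of MDS, CMML and AML, IWG 2000 criteria, bilineage HI, and evaluability limited to patients with four or more cycles. It illustrates a share and does not predict one.

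**The case against.** The strongest reply is that the endpoint-specific text settles the ORR. HI is named as a response in the synopsis, 13.1 and 13.4, and the separate HI rate promised in 13.4 cannot be produced unless HI is assessed in each patient. Section 13.5.2 reads as general wording and never lists which categories are responses. Appendices A1 and A2 are separate tables, so a patient can be stable disease on the first and an HI responder on the second.

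This stands as far as the ORR goes. A reader might infer that the ORR and its two-response rule cannot be derived, or that the trial's power falls from .84 to .47. The documents support neither. The ORR can be obtained by counting patients with CR, PR or HI, and the lower figure needs both a CR+PR count that no section calls for and an assumed 50% HI share. Nor are HI-only patients scored as failures, since stable disease lies outside categories 4-9.

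The reply does not remove the conflict. Section 13.5.2 requires one category per patient and describes itself as covering the main response analysis, and nothing says that 13.4 overrides it. Nothing in 13.4 repairs the duration definition.

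It is also fair that response duration is exploratory, and that no test, sample size or stopping rule depends on it. That limits severity.

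**Conclusion.** The plan is inconsistent, at moderate severity. The certain effect, on the text as written, is that median response duration omits HI-only responders who count in the ORR. With about 3 to 4 responders expected at a 15% ORR, losing even one changes that estimate materially. The second effect is a conflict between 13.5.2 and 13.4 over patient-level responder status, which carries into the biomarker comparisons.

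The ORR is not necessarily understated. The reduced probabilities in the table apply only if responses are read from 13.5.2 as CR plus PR, and they rest on a true combined rate of 15% and an assumed HI share.

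**What to change.** **Section 13.5.2.** Add a category for hematologic improvement by Appendix A2 without CR or PR, and count it as a response. State that CR, PR and this category make up the ORR and that the definition in 13.4 governs, including for the MDSC and PD-L1 comparisons. The words *without CR or PR* also prevent a patient who meets both HI and CR or PR from being counted twice when rates are summed.

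**Section 11.2.** Measure duration from the first CR, PR or HI to the first of: relapse after CR or PR (Appendix A1), progression or relapse after HI (Appendix A2), or disease progression. State which loss criterion applies when HI is followed by CR or PR. The two differ: Appendix A1 includes return of marrow blasts to the pretreatment level, and Appendix A2 allows for other explanations such as infection or bleeding. One workable choice is to let the best category reached decide. Report duration for the CR/PR subset separately.

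**Cost.** A few lines in two sections and probably one response code. The case report form is not in the documents, so that last item cannot be confirmed. Sample size, decision rule and visit schedule do not change, and 13.4 already requires HI to be assessed. The wording should be settled before response data are reviewed.

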14. STUDY STATUS UPDATES AND STUDY CLOSURE

14.1 Definitions of Study Status Changes

14.1.1 Temporarily Closed to Accrual

The study status is Temporarily Closed to Accrual when no patient slots are currently available, but there is the possibility that the trial will re-open for accrual (patient slots become available). Sites are not permitted to accrue additional patients until CTEP is notified of Re-Activation.

Study status will need to be changed to Temporarily Closed to Accrual when any of the following criteria are met:

- Sites are notified by CTEP (via Request for Rapid Amendment [RRA]) of changes in the risk/benefit ratio that necessitate changes to the patient Informed Consent document. Requested changes will be specified in the RRA and must be reviewed by the study's IRB.
- CTEP and the lead investigator agree that unacceptable toxicities necessitate a discussion to change the dosing/regimen.
- A protocol-defined benchmark has been achieved (such as an interim analysis before proceeding to the next stage).
- Investigators encounter any of the stopping criteria described in Section 5.3.

14.1.2 Closed to Accrual

The study status is (permanently) Closed to Accrual when no more patient enrollment slots are available, and at least one patient is still actively receiving the study treatment. Sites are no longer permitted to enroll additional patients.

Patient slots are no longer available when the following criteria are met:

- The pre-specified number of evaluable patients has been successfully enrolled, treated, and evaluated.
- The study treatment has failed to meet the pre-specified efficacy goal at the stage 1 interim analysis.
- CTEP and the investigators agree that unacceptable toxicities preclude further enrollment.
- Investigators encounter any of the stopping criteria described in Section 5.3.

14.1.3 Closed to Accrual and Treatment

The study status is Closed to Accrual and Treatment when no more patient enrollment slots are available and no patients are currently receiving the study treatment. Patients may still be enrolled on the protocol only for the purposes of follow-up.

Patient accrual and treatment will be permanently halted when any of the following criteria are met:

- Enrollment was previously closed (study status of “Closed to Accrual”), and no patients are receiving the study treatment.
- CTEP and the investigators agree that unacceptable toxicities preclude further enrollment. In this case, CTEP and the investigators must collaborate to alter the regimen or to halt the study treatment altogether as soon as it can be safely done for patients currently receiving treatment.

CTEP and Theradex **must be notified** when patients are no longer receiving treatment [*i.e.*, when the last patient(s) to be receiving treatment is/are no longer receiving the study regimen for any reason].

